Regional or General Anesthesia for Post-operative Delirium in Patients Undergoing Hip Fracture Surgery

Abbreviations: RAGA-Delirium

Clinical trails No.: NCT02213380

Unit Leader: 01 Second Affiliated Hospital of Wenzhou Medical University

Participants:02 Tongji Hospital, Huazhong University of Science and Technology

03 West China Hospital, Sichuan University

First Affiliated Hospital of Third Military Medical University

(Southwest Hospital)

05 First Affiliated Hospital of Wenzhou Medical University

06 Second Affiliated Hospital of Zhejiang University Medical

College

07 Beijing Jishuitan Hospital

08 First Affiliated Hospital of Nanchang University

09 Second Affiliated Hospital of Anhui Medical University

10 Ningbo Second People's Hospital

11 Taizhou Hospital, Zhejiang Province

12 Lishui People's Hospital

Option number: 1.1 8 July 2014

Confidentiality statement

The clinical research thinking, data, and other relevant information in this document are owned by the Second Affiliated Hospital of Wenzhou Medical University. We allow the research unit members, the ethics committee, and other clinical research-related institutions to read. Do not leak this plan without the consent of the team leader!

Program summary

| | |
|----------------------|--|
| Name of study | Prospective, multicenter, large sample, randomized controlled study of the effect of local and general anesthesia on postoperative delirium in elderly patients with hip fractures |
| Purpose of the study | To evaluate the effect of two anesthetic methods on the incidence and prognosis of delirium in elderly hip fracture |
| Clinical trial units | 
Clinical trial leader: 01 Second Affiliated Hospital of Wenzhou Medical University
 
Clinical trial participants: 02 Tongji Hospital, Huazhong University of Science and Technology 03 West China Hospital, Sichuan University First Affiliated Hospital of Third Military Medical University (Southwest Hospital) 05 First Affiliated Hospital of Wenzhou Medical University 06 Second Affiliated Hospital of Zhejiang University Medical College 07 Beijing Jishuitan Hospital 08 First Affiliated Hospital of Nanchang University 09 Second Affiliated Hospital of Anhui Medical University 10 Ningbo Second People's Hospital 11 Taizhou Hospital, Zhejiang Province 12 Lishui People's Hospital
 |
| Research Design | Prospective, multicenter, large sample, randomized controlled study design |
| Research population | Elderly patients with acute hip fractures on one side requiring surgical treatment |
| Selection criteria | 
 1. age greater than or equal to 65 2. ASA I ~ IV 3. Voluntary signature of informed consent |
| Exclusion criteria | 
 1. complex 1. injuries: multiple fractures, chest, abdomen, pelvic and sacral trauma, head trauma, etc 2. contraindications of intraspinal anesthesia: coagulation dysfunction, thrombocytopenia, intraspinal space-occupying, infection of the puncture site, etc 3. relative contraindications of general anesthesia: known difficult airway, malignant hyperthermia, etc 4. nerve block taboo: puncture site infection, peripheral neuropathy, local anesthetic allergy, etc |

| | |
|------------------------|--|
| | 5. have participated in other clinical studies |
| Research Groups | 1. local anesthesia group (RA group) 2. general anesthesia group (GA group) |
| Main indicators | Incidence of delirium within 7 days after the operation |
| Secondary indicators | Type, severity, duration of 1. delirium (DRS-R-98 scale diagnosis); 2. postoperative pain score (pain VAS score); 3. other related complications and outcomes: related complications: pulmonary infection, myocardial infarction, renal failure, gastrointestinal bleeding; 4. length of stay; 5. mortality rates during hospitalization and 30 days after surgery; 6. the total cost of hospitalization and anesthesia; Follow-up for 6 months and 1 year of 7. discharge: incidence, type, severity, cognitive function, quality of life, mental condition, the mortality of delirium. |
| Statistical analysis | Comparison of incidence of delirium, degree of delirium, type of delirium, and prognosis of patients |
| Expected test progress | 2 years |

Directory

| | | |
|-------|---|----|
| | Programme summary..... | 3 |
| 1. | Background and significance of the study..... | 6 |
| 2. | Research topics..... | 9 |
| 3. | Purpose of study..... | 9 |
| 4. | Research Design..... | 9 |
| 5. | Case selection..... | 9 |
| 5.1 | Research population..... | 9 |
| 5.2 | Selection criteria..... | 9 |
| 5.3 | Exclusion criteria..... | 9 |
| 5.4 | Termination criteria..... | 10 |
| 5.4.1 | Patient standard..... | 10 |
| 5.4.2 | Research Standards..... | 10 |
| 6. | Random grouping..... | 10 |
| 7. | Anaesthesia:..... | 11 |
| 8. | Main indicators:..... | 12 |
| 9. | Secondary indicators:..... | 12 |
| 10. | Data collection..... | 14 |
| 11. | Technical route:..... | 15 |
| 12. | Adverse event reports..... | 17 |
| 12.1 | Adverse events..... | 17 |
| 12.2 | Serious adverse events..... | 18 |
| 13. | Data management and statistical analysis..... | 20 |
| 14. | Test management..... | 22 |
| 15. | Test quality control..... | 19 |
| 16. | Data preservation..... | 20 |
| 17. | Publication of papers..... | 20 |
| 18. | References..... | 20 |

1. Background and significance of the study

Delirium, also known as acute consciousness disorder, is an acute organic brain syndrome with attention, feeling, thinking, memory, mental exercise, and sleep cycle disorders occurring in a short period, characterized by restlessness, multilingualism, orientation disorders, and unanswered questions. Age (≥ 65) and hip fractures are major risk factors for delirium. The incidence of delirium in elderly inpatients was reported in 14%~56%, while in elderly patients with hip fractures, the incidence of delirium was 32%~53.3% higher. An incidence of postoperative delirium was reported in 11.1%~44.8% in elderly patients. The incidence of postoperative delirium was higher in 20.3%~60.9% in elderly patients with hip fractures. After delirium occurs, diazepam or psychotic drugs are often needed to increase nursing requirements and the risk of falling while delaying the time of autonomous activity and hospital stay and increasing medical costs. During recovery, delirium increases mortality (figure 1), and disability can also increase the incidence of dementia. Dysfunction also causes persistent depression or anxiety.

Elderly patients are prone to low-activity delirium, which is not easy to detect and is easily misdiagnosed as cognitive decline, depression, or dementia. Han results suggest that low activity type is very common in the emergency department, 76% of which are missed by emergency doctors. Ouimet et al. found that delirium incidence was 70%, 2/3 of delirium was poor, mortality was higher, and high activity outcome was generally better, which was closely related to low activity type identification and misdiagnosis. Mixed delirium (alternate low activity and high activity) is severe, and cognitive impairment is more severe. However, some studies have suggested that the prognosis of low active delirium in elderly patients with hip fracture is higher than that of active delirium. There are many reasons for misdiagnosis or missed diagnosis of delirium, one of which is that clinicians pay less attention to delirium and often underestimate the incidence, severity, and delirium outcome. A British questionnaire found that young doctors lack the basic knowledge of diagnosis and management of delirium and lack understanding of the prevalence and clinical significance of delirium. Delirium is traditionally considered a temporary disease, but there is growing evidence that delirium is often persistent, poor after recovery, and increases dementia and cognitive impairment. Coler, a systematic review of 18 prospective studies, found continuous delirium common at discharge; the rate is 44.7%, The incidence of delirium was 32.8%, 25.6%, and 21% in 1, 3 and 6 months after discharge; poor prognosis in mortality, function, and consciousness in patients with persistent delirium. Dasgupta's systematic review found, Continuous delirium is

associated with hypoactive delirium, Can increase the severity of delirium, Cognitive impairment, Causes many kinds of complications and so on; Meanwhile, The author also believes that the existing information can not fully explain this problem .

One of the important medical interference methods in treating patients by anesthesia surgery is closely related to delirium occurrence and development. There are few studies on the relationship between anesthesia and delirium, which can reduce the incidence of delirium. Although simple local anesthesia avoids the disturbance of general anesthesia to patients' mental state, it has not been confirmed whether to reduce delirium. Sieber etc Shallow sedation (BIS BIS<80) reduced the incidence and duration of postoperative delirium compared with deep sedation (BIS<50) in elderly patients with hip fractures. However, at home, Yue waited It was found that general anesthesia with different anesthetic depth and mode had no significant effect on early delirium incidence in patients with hip arthroplasty. Tan Gang, China, The results of epidemiological investigation of postoperative delirium in elderly patients with non-cardiac surgery showed that general anesthesia was not a risk factor for delirium; the risk factors related to anesthesia were the occurrence of perioperative hypotension, the use of scopolamine and pethidine. Abou-Setta etc. The results showed that local nerve block analgesia did not reduce postoperative delirium incidence. Mouzopoulos and A randomized controlled study of iliac fascia block and perioperative delirium in hip fracture showed that iliac fascia block reduced delirium incidence compared with placebo. Clegg and Young Studies on different drugs and delirium suggest that opioids, benzodiazepines, and blood pressure-lowering drugs dihydropyridine can increase delirium incidence. However, the authors also stress insufficient evidence to support it. Lonergan etc. A study of ICU patients suggested that lorazepam increased delirium interval compared with dexmedetomidine. The results did not suggest that benzodiazepines could be used to treat delirium.

Current Vague Assessment Scale of Consciousness (Confusion Assessment Method, CAM) It is still the most widely used delirium diagnostic tool for non-psychiatric specialists. Its items are simple, accurate, and easy to use. It is widely used in clinical and research. The limitation is that patients with language disorders can not be assessed, it is difficult to distinguish delirium from dementia, depression, or other mental illness, and the severity of delirium can not be assessed, so it is difficult to grasp the fluctuation of the condition dynamically. CAM-ICU scale. Has been shown to be used to diagnose delirium in patients with severe ICU tracheal intubation or verbal communication. Its multi-language translations, including Chinese versions, have also been shown to have high reliability and validity in clinical

applications. The CAM-ICU scale has been proved to be effective in the diagnosis of postoperative delirium in the recovery room (PACU) of anesthesiology. The recent review of delirium emphasizes that patients with delirium should be classified into exercise subtypes, the severity of delirium should be assessed, and the fluctuation of delirium should be dynamically monitored, which is beneficial to the diagnosis of etiology, treatment, cognitive impairment and outcome. At present, there is a delirium rating scale (Delirium Rating Scale, DRS), delirium rating scale-98 revised edition (DRS-R-98), memory delirium evaluation scale (Memorial Delirium Assessment Scale, MDAS) and so on. DRS-R-98 delirium scale. It is considered to be an effective and credible delirium severity scale; it can be used to distinguish delirium from other mental disorders such as Alzheimer's disease, schizophrenia, and depression, to classify delirium and to continuously observe the changes of delirium patients' condition. The scale has been translated into Chinese and confirmed to have high reliability and validity.

This study's significance is to observe and compare the effects of general anesthesia and local anesthesia on delirium and other related complications after hip fracture in the elderly through prospective, large sample, multicenter and randomized controlled clinical studies. The following questions are identified:

- 1) Is there any difference between general anesthesia and local anesthesia in the occurrence, severity, attack type, and delirium duration after hip fracture in the elderly? Which anesthetic method can reduce the incidence of postoperative delirium?
- 2) Is there a difference in the effect of the two anesthetic methods on postoperative delirium in different older people (elderly, dementia, or delirium)?
- 3) Do various factors (hypotension, drugs, pain, etc.) during anesthesia affect postoperative delirium and extent?
- 4) To analyze whether the control of anesthesia can reduce the medical expenses and related economic benefits caused by delirium.
- 5) The relationship between the classification and duration of delirium and patients' prognosis; does delirium lead to long-term cognitive dysfunction? How does it affect patients and their families' quality of life? The survival rate in patients with delirium?

2. Research topics

A randomized, controlled, multicenter, prospective study of the effect of local and general anesthesia on postoperative delirium in elderly patients with hip fractures

3. Purpose of the study

To evaluate the effect of two anesthetic methods on the incidence and prognosis of delirium in elderly hip fracture

4. Research Design

using prospective, multicenter, large sample, randomized controlled study design. Randomly enter local anesthesia group or general anesthesia group at 1:1.

According to the domestic literature report of postoperative delirium in elderly patients, the sample size estimation estimated that postoperative delirium incidence is about 26. Assuming that postoperative delirium incidence after local anesthesia is less than 30% of general anesthesia, the calculated sample size is 441 $n\alpha=$ each group. The provisional total sample size is 1000 cases. The sample size can be adjusted according to the progress of the study and the results in the medium term.

The number of cases in each center is 100. Because of the central random system, the number of cases in each center can be automatically adjusted according to the actual situation of the subjects recruited.

5. Case selection

5.1 Research population

Elderly patients with acute (≤ 3 weeks) hip fractures on one side need surgical treatment.

5.2 Selection criteria

- 1) Age greater than or equal to 65
- 2) ASA I ~ IV
- 3) Voluntary signature of informed consent

5.3 Exclusion criteria

- 1) Compound injury: multiple fractures, chest, abdomen, pelvic and

sacral trauma, head trauma, etc.

- 2) Intravertebral anesthesia contraindications: coagulation dysfunction, thrombocytopenia, intraspinal space-occupying, puncture site infection, etc.
- 3) relative contraindications of general anesthesia: known difficult airway, malignant hyperthermia, etc.
- 4) Nerve block contraindication: puncture site infection, peripheral neuropathy, local anesthetic allergy and so on.
- 5) Have participated in other clinical studies.

5.4 Termination criteria

5.4.1 Patient standard

5.4.1.1 Subject may withdraw from the study at any time without giving any explanation and without losing the right to future medical care;

5.4.2 Research Standards

5.4.2.1 Use of drugs in violation of program requirements during observation;

5.4.2.2 Other conditions that may increase the risk of the patient;

5.4.2.3 serious complications occurred during observation.

6. **Random grouping**

After obtaining informed consent, all selected patients were randomly grouped by network or telephone central random system (1 : 1):

- 1) local anesthesia group (RA group): epidural anesthesia, lumbar anesthesia, combined spinal anesthesia, nerve block (but the failure rate is high, not recommended).
- 2) General anesthesia group (GA group): general anesthesia + nerve block, general anesthesia, intraspinal anesthesia, simple general anesthesia.

7. Anesthesia:

Because of the particularity of senile anesthesia, experienced anesthesiologists are required to carry out anesthesia. They need to master nerve block, intraspinal anesthesia, and general anesthesia and be competent for anesthesia in elderly hip fracture surgery.

- 1) Preoperative, intraoperative, and postoperative patients were prevented from using any sedative drugs other than intravenous anesthetics (e.g., midazolam, dexmedetomidine, etc.) if surgical reasons for postoperative use of sedative drugs should be recorded in detail.
- 2) General anesthesia group, propofol or etomidate intravenous induction, anesthesia should be as simple as possible. Drugs such as ephedrine, opioids, atropine, and other drugs that have a certain impact on the spirit of consciousness should be used with clinical indications and recorded on the CRF table. All-body anesthesia can be performed before completing the nerve obstruction lag (or before), laryngeal mask, tracheal intubation, or mask can be passed through, mechanical ventilation, or spontaneous ventilation. Intraoperative use of intravenous analgesics, inhalation anesthesia (sevoflurane or isoflurane), or intravenous anesthesia to maintain general anesthesia. Iliac fascia block "3 in1" block, femoral nerve block, or posterior lumbar plexus block; single nerve block or a continuous nerve block can be used.
- 3) The local anesthesia group can use nerve block analgesia before operation (anterior femoral nerve or iliac fascia block is recommended to relieve pain in position) or opioid drugs (avoid pethidine), and then epidural anesthesia, lumbar anesthesia, or combined spinal anesthesia puncture. Do not use sedation techniques and related adjuvant sedation drugs. If sedative drugs

are used for surgical or other reasons, please record them in detail.

- 4) Intraoperative anesthesia management: if the anesthetic effect of the local anesthesia group can not complete the operation, the anesthesiologist can decide to use the drug or change the general anesthesia and record it in detail. This study does not make any provision for this situation. The general anesthesia group adjusted the depth of general anesthesia according to the surgical stimulation. Blood pressure reduction base value 30% or systolic blood pressure less than 90 mmHg is hypotension, recommended for vasoactive drugs or liquid treatment, the anesthesiologist can be appropriate according to personal experience.
- 5) Postoperative analgesia: various analgesia methods can be used (intravenous, epidural, nerve block sustained or self-controlled analgesia, or combined with oral medication), but both groups avoid using any sedative.

Considering the actual situation and the particularity of geriatric anesthesia, it is estimated that there will be some differences in the implementation of anesthesia, puncture technique, and intraoperative management among the research centers and anesthesiologists. The scheme does not provide for these differences or differences.

8. Main indicators:

Incidence of delirium within 7 days after surgery (CAM)

9. Secondary indicators:

- 1) Delirium type, severity, duration (diagnosed by DRS-R-98 scale)
- 2) Postoperative pain score VAS pain score)
- 3) Other related complications and outcomes: related complications: pulmonary infection, myocardial infarction, renal failure,

gastrointestinal bleeding;

- 4) Hospitalization time
- 5) The mortality rate during hospitalization and 30 days after surgery
- 6) The total cost of hospitalization and anesthesia.
- 7) 6 months and 1-year follow-up: incidence, type, severity, the cognitive function of delirium (mini-mental state examination, MMSE), quality of life (The MOS 36-item Short-Form Health Survey, SF-36) Hospital Anxiety and depression scale, HADS mental state), mortality.

Description:

The incidence of delirium before surgery includes (delirium from admission to surgery). CAM scale is used for the diagnosis of delirium in the ward; the CAM-ICU scale is used to diagnose delirium in the intensive care unit, that is, CAM-ICU is used when the CAM is not available. When there is a contradiction between the diagnosis obtained by the scale and the psychiatrist's diagnosis, when there are still differences after consultation, the diagnosis of the psychiatrist shall prevail. To prevent missed diagnosis, we should communicate with the medical staff in the ward on time. After the patient is selected, the family member or escort staff should be informed. The researcher should be informed of the evaluation of delirium when any abnormal performance of the patient's mood, consciousness, cognition and so on is found. When postoperative delirium is found, the subject should communicate with the competent physician and decide on further diagnosis and treatment if the patient's performance was normal 7 d after the operation, the visit ended, while the patient with continuous delirium was followed up until normal or discharged. Delirium patients were assessed by delirium rating scale 98 revised (DRS-R-98) for type and severity of delirium. The patient's assessment form was used as evidence of postoperative delirium and the duration of delirium.

10. Data collection

Arrange post-operative delirium assessment and data collection by a fixed staff member who should not know about the study design and purpose to reduce the error in the study report, assess the presence, type, severity of postoperative delirium daily, patient medical records and nurse records are also used to determine whether delirium occurs for a total of 7 days after surgery (delirium was observed and discharged). The data collection table is shown in Table 1. Besides, the mortality, hospitalization time, and discharge department were recorded. Table 2 summarizes other data to be collected.

Table 1 Data collected daily. P: days after surgery

| Time points | Preoperative evaluation | P1 | P2 | P3 | P4 | P5 | P6 | P7 |
|---|-------------------------|----|----|----|----|----|----|----|
| Temperature | * | * | * | * | * | * | * | * |
| Blood pressure | * | * | * | * | * | * | * | * |
| Heart rate | * | * | * | * | * | * | * | * |
| Oxygen saturation | * | * | * | * | * | * | * | * |
| Hemoglobin | * | * | * | * | * | * | * | * |
| Alanine aminotransferase | * | * | * | * | * | * | * | * |
| Alanine aminotransferase | * | * | * | * | * | * | * | * |
| Album | * | * | * | * | * | * | * | * |
| Urea nitrogen | * | * | * | * | * | * | * | * |
| Creatinine | * | * | * | * | * | * | * | * |
| PH | * | * | * | * | * | * | * | * |
| PO2 | * | * | * | * | * | * | * | * |
| PCO2 | * | * | * | * | * | * | * | * |
| HCO3 | * | * | * | * | * | * | * | * |
| Na | * | * | * | * | * | * | * | * |
| K | * | * | * | * | * | * | * | * |
| Cl | * | * | * | * | * | * | * | * |
| Delirium CAM or not | * | * | * | * | * | * | * | * |
| DRS-R-98 of type and severity of delirium | * | * | * | * | * | * | * | * |
| VAS pain score | * | * | * | * | * | * | * | * |

Table 2: Other data to be collected

| Period | Data | Method |
|---------------------------|--|--|
| Preoperative general data | Age, sex, address, type of fracture History, ASA rating Cognitive function (MMES) | Medical records MMSE |
| Intraoperative | Methods of operation, level of the surgeon, manner of anesthesia Anesthesiologist level, anesthetic substance, and dosage Low blood pressure | Review of medical records and anesthesia records |

| | | |
|------------------------------|---|--|
| | Duration of operation estimated blood loss | |
| Postoperative | Length of stay, hospitalization costs, anesthesia costs, adverse events, mortality during hospitalization,30-day mortality, withdrawal from the study | Telephone follow-up |
| 6 months and 12 months later | Whether delirium occurs, type and severity Mortality Quality of life, anxiety or depression | Quality of life scale SF-36, anxiety and depression scale (HADS) Review of patients' families |

11. Adverse event reports

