4.6 Analysis Populations

All analyses of primary and secondary outcomes, including safety outcomes, will be based on intention-to-treat. Participants would be analysed in the intervention group to which were randomised, and all participants shall be included whether or not they received the allocated intervention.

As a sensitivity analysis, a per-protocol analysis would also be carried out for the primary outcome and secondary outcomes.

5. Definition and Derived variables

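### Protocol 5.4.2 lets a serious complication terminate a case, and neither document says that outcome assessment continues afterwards

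*Protocol*

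**What the plan says.** Protocol section 5, on case selection, contains "5.4 Termination criteria". Its patient part (5.4.1) is withdrawal: "Subject may withdraw from the study at any time without giving any explanation". Directly below, 5.4.2 adds three further criteria: use of drugs against the protocol, other conditions that may add to the patient's risk, and "5.4.2.3 serious complications occurred during observation". The Protocol does not define what is terminated. Neither document says what happens to outcome assessment afterwards.

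Other sections need data from the same patients:

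- Protocol section 8 makes CAM delirium within 7 days of surgery the primary endpoint.
- Protocol section 9 lists "related complications: pulmonary infection, myocardial infarction, renal failure" and gastrointestinal bleeding as outcomes, then "The mortality rate during hospitalization and 30 days after surgery", then delirium, cognition, quality of life, mood and mortality at 6 months and 1 year.
- The description after section 9 provides CAM-ICU for patients in intensive care.
- Protocol section 7 asks for any sedative use to be recorded in detail.
- SAP 4.6 analyses by intention to treat: "all participants shall be included whether or not they received the allocated intervention".

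**The concern.** The randomised intervention is one anaesthetic, which is over before the daily assessments on postoperative days 1 to 7 (P1 to P7) begin. A criterion that operates during observation therefore bears mainly on what happens to follow-up. If a site takes termination to mean leaving the study, as the neighbouring withdrawal item suggests, CAM and the 30-day, 6-month and 12-month contacts can stop because the patient became seriously ill.

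That would be informative loss: the reason for missingness is a post-randomisation event related to delirium and death, and possibly to the anaesthetic. An intention-to-treat rule keeps patients in the analysis but cannot supply assessments that were never made. Sites may also read 5.4.2 differently, so the loss could vary by centre.

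**Working it through.** **1. Does the text permit the loss?** Section 5.4 sits within case selection and its items speak of the patient, so it acts on individual cases. Protocol 12.4.2(1) plans to compare drop-out overall and drop-out due to adverse events, so such exits are expected. SAP 6.1 plans to report reasons for loss of primary outcome data. On the other side stand CAM-ICU, the follow-up of persistent delirium to recovery or discharge, adverse event tracking (Protocol 11.1 and 11.2) and SAP 4.6. None of these says that CAM or the later contacts continue after termination.

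**2. What would the analysis do with the gap?** Protocol 12.4.1 carries the last observation forward (LOCF), so a patient stopped while CAM-negative counts as free of delirium. SAP 4.5 imputes nothing, and SAP 4.4.2 keeps anyone with one post-randomisation efficacy assessment. Neither recovers the unseen events.

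**3. The plan's own figure.** Inputs from SAP 3.3: 26% under general anaesthesia (GA), a 30% reduction under regional anaesthesia (RA), so 0.26 × 0.70 = 18.2%; 80% power; two-sided 5%.

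n = (1.960 + 0.842)² × (0.26×0.74 + 0.182×0.818) / 0.078², rounded up = 441 per group. This reproduces the stated figure. Allowing 10% drop-out, 441/0.90 = 490 per arm, or 980, which the plan rounds to 1000.

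Power = Φ{[d√n − 1.96√(2p̄(1−p̄))] / √(p₁(1−p₁)+p₂(1−p₂))}, where d = p₁ − p₂ and p̄ is their mean. It is 0.845 with 500 per arm and 0.806 with 450 per arm (after 10% drop-out).

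**4. Equal stopping (assumed inputs).** Let c be the share of each arm stopped before delirium is seen, and k their delirium risk relative to the others. Neither is in the documents.

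- Rate among those retained = p / (1 − c + ck).
- Share of events lost = ck / (1 − c + ck).
- For c = 10%, k = 2: 0.26/1.10 = 23.6%, 0.182/1.10 = 16.5%, events lost 0.20/1.10 = 18.2%.
- For c = 10%, k = 3: 0.26/1.20 = 21.7%, 0.182/1.20 = 15.2%, events lost 0.30/1.20 = 25%.

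| c | k | Events lost | Power, not imputed | Power, LOCF |
|---|---|---|---|---|
| 5% | 2 | 9.5% | 0.76 | 0.755 |
| 10% | 2 | 18.2% | 0.71 | 0.70 |
| 10% | 3 | 25% | 0.67 | 0.66 |
| 20% | 3 | 43% | 0.54 | 0.52 |

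These figures come on top of the 10% drop-out: 450(1 − c) per arm without imputation, 450 with LOCF. The relative risk (RR, RA to GA) stays at 0.70 because the loss is equal.

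**5. Unequal stopping (assumed inputs).** Without imputation, observed RR = true RR × (1 − c_GA + c_GA·k) / (1 − c_RA + c_RA·k). LOCF multiplies this by (1 − c_RA)/(1 − c_GA).

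- GA 10%, RA 5%, true RR 1.00: 1.10/1.05 = 1.05 (k = 2) and 1.20/1.10 = 1.09 (k = 3). With LOCF, × 0.95/0.90 gives 1.11 and 1.15.
- Same stopping, true RR 0.70: 0.73 to 0.76, or 0.77 to 0.81 with LOCF.
- Arms swapped, true RR 1.00: 1.05/1.10 = 0.95 and 1.10/1.20 = 0.92.

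**The case against.** The strongest reply is that termination is undefined and need not mean the end of assessment. Some protocol-directed management does continue after surgery: both groups are to avoid sedatives during postoperative analgesia (Protocol section 7). Ending that restriction is a coherent reading of 5.4.2. CAM-ICU presupposes that very ill patients are assessed, and Protocol section 10 also uses medical and nursing records to determine delirium over the 7 days. SAP 4.4.3 deals with deviations by exclusion from the per-protocol set only. This stands, and it makes the point an unresolved contradiction rather than a settled rule to stop observing.

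A reader might go further and infer that the trial loses its complication endpoint and most of its deaths. The documents do not support that. Adverse events are tracked until remission or stability, life-threatening events and deaths are serious adverse events reportable within 24 hours, and Table 2 lists in-hospital and 30-day mortality together with withdrawal as items to collect. The triggering complication, and probably a death from it, would be captured. Nor does either document say what share of delirium events or deaths arises in such patients.

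The illustration is also a worst case for timing, because CAM is daily from P1 and delirium seen before termination still counts. If the planned 10% drop-out already consists of these patients, 450 per arm remain and power is 0.76 (k = 2) or 0.71 (k = 3), not 0.71 or 0.67.

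**Conclusion.** The point holds as a gap that permits informative loss. Three kinds of post-randomisation event are grounds for terminating a case, and nothing protects outcome collection after them. At risk are later CAM results, later complications and the 6- and 12-month outcomes, with 30-day mortality affected to a lesser extent.

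Size and direction cannot be determined from the documents. Every figure in steps 4 and 5 rests on an assumed stopped share and an assumed relative delirium risk. Equal stopping costs power and understates incidence in both arms but leaves the RR intact. Unequal stopping biases the RR, and its sign depends on which arm loses more. It would therefore be wrong to claim that the rule favours one anaesthetic. The stated sample size is unaffected and reproduces. The matter deserves an amendment because missed daily assessments cannot be repeated later.

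**What to change.** Reconcile Protocol 5.4.2 with sections 7 to 9, the description of CAM-ICU assessment and SAP 4.6. State that meeting a 5.4.2 criterion is recorded as an event or deviation and does not by itself end outcome collection. Scheduled CAM or CAM-ICU to P7 and the 30-day, 6-month and 12-month contacts then continue for every randomised patient unless consent to data collection is withdrawn. The criteria themselves, clinical management and any decision to end protocol-directed care stay with the sponsor and the treating team.

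The cost is one paragraph, submitted for ethics approval as Protocol 13.2 requires. It adds no assessments, since it keeps those already scheduled. The small downside is that some are made in sicker patients, for whom CAM-ICU is already provided. The amendment does not settle LOCF against no imputation; the two documents still need one rule for whatever data remain missing.
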